7.1.6 Supportive analyses

Commercially Confidential Information

Longitudinal analysis will firstly include individual and average graphical presentations over time incorporating any historical LDH data collected so as to better put post-treatment changes in context. If deemed potentially useful, longitudinal statistical modelling will be used to look at changes within subjects as well as across subjects.

Additionally serum LDH at each timepoint will also be summarized in terms of the number and percentage of patients achieving a reduction in LDH to within the normal limits.

7.2 Secondary objectives

The analysis of the two secondary endpoints of standard safety monitoring with increased vigilance for infections and measurement of serum concentrations of LFG316 are covered in Section 8.1.2 (adverse events) and Section 6 (pharmacokinetics) respectively. There will be no adjustment for multiplicity over the three main analyses of efficacy (primary), safety and PK (both secondary).

7.3 Exploratory objectives

Commercially Confidential Information

Commercially Confidential Information

8 Statistical methods for safety and tolerability data

8.1.1 Variables

Adverse events, vital signs (blood pressure, pulse rate, body temperature), ECG intervals, laboratory measurements, as well as subject demographics and baseline characteristics will be listed, summarized and plotted.

8.1.2 Descriptive analyses

Subject demographics and other baseline characteristics

All data for background and demographic variables will be listed by ethnicity, C5 variant status and patient. Summary statistics will be provided.

Relevant medical history, current medical conditions, results of laboratory screens, drug tests and any other relevant information will be listed by ethnicity and C5 variant status and summarized.

Treatment

Data for study drug administration, and concomitant therapies will be listed by ethnicity and C5 variant status and summarized.

Vital signs

All vital signs data will be listed by ethnicity, C5 variant status and patient and visit/time and if ranges are available abnormalities (and relevant orthostatic changes) will be flagged. Summary statistics will be provided over visit/time.

ECG evaluations

All ECG data will be listed by ethnicity, C5 variant status and patient and visit/time, and abnormalities will be flagged. Summary statistics will be provided over visit/time.

Clinical laboratory evaluations

All laboratory data will be listed by ethnicity, C5 variant status and patient and visit/time and if normal ranges are available abnormalities will be flagged. A separate listing is provided presenting all parameters in a patient with any abnormal values. Summary statistics will be provided over visit/time.

Adverse events

All information obtained on adverse events will be listed by ethnicity and C5 variant status and displayed summarized as per the secondary objective.

The number and percentage of patients with adverse events will be tabulated by body system and preferred term. A patient with multiple adverse events within a body system is only counted once towards the total of this body system.

As this study has four treatment periods an adverse event starting in one period and continuing into another is counted only in the first period grouping in which it occurs. A patient with multiple adverse events within a body system and treatment period is only counted once towards the total of this body system and treatment period. There will be three types of summaries of AEs, starting in periods 1 to 3, starting in period 4, and overall throughout the study.

Pregnancy test

All pregnancy test results for women will be listed by ethnicity, C5 variant status, patient and visit.

Commercially Confidential Information

Other safety evaluations

All other safety evaluations e.g. physical examination will be listed by ethnicity, C5 variant status, patient and visit.

Meningococcal vaccination data will be listed by ethnicity, C5 variant status and patient.

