9.1 Adverse events

An adverse event (AE) is any untoward medical occurrence (i.e., any unfavorable and unintended sign [including abnormal laboratory findings], symptom or disease) in a subject or clinical investigation subject *after providing written informed consent* for participation in the study. Therefore, an AE may or may not be temporally or causally associated with the use of a medicinal (investigational) product.

The occurrence of adverse events should be sought by non-directive questioning of the subject at each visit during the study. Adverse events also may be detected when they are volunteered by the subject during or between visits or through physical examination, laboratory test, or other assessments.

Abnormal laboratory values or test results constitute adverse events only if they fulfill at least one of the following criteria:

- they induce clinical signs or symptoms,
- they are considered clinically significant,
- they require therapy.

Clinically significant abnormal laboratory values or test results should be identified through a review of values outside of normal ranges/clinically notable ranges, significant changes from baseline or the previous visit, or values which are considered to be non-typical in patients with underlying disease. Investigators have the responsibility for managing the safety of individual subject and identifying adverse events. Alert ranges for liver related events are included in [Section 9.3](#).

Adverse events must be recorded on the Adverse Events CRF pages for subjects that pass screening and enter into the study. The adverse events should be reported according to the signs, symptoms or diagnosis associated with them, and accompanied by the following information:

1. the severity grade
 - mild: usually transient in nature and generally not interfering with normal activities
 - moderate: sufficiently discomforting to interfere with normal activities
 - severe: prevents normal activities
2. its relationship to the study treatment (no/yes)
3. its duration (start and end dates) or if the event is ongoing an outcome of not recovered/not resolved should be reported.
4. whether it constitutes a serious adverse event (SAE) See [Section 9.2](#) for definition of SAE

5. action taken regarding [study/investigational] treatment(select as appropriate).

All adverse events should be treated appropriately. Treatment may include one or more of the following:

- no action taken (i.e. further observation only)

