- study treatment dosage adjusted/temporarily interrupted
- study treatment permanently discontinued due to this adverse event
- concomitant medication given
- non-drug therapy given
- subject hospitalized/subject's hospitalization prolonged

6. its outcome (not recovered/not resolved; recovered/resolved; recovering/resolving, recovered/resolved with sequelae; fatal; or unknown)

Once an adverse event is detected, it should be followed until its resolution or until it is judged to be permanent, and assessment should be made at each visit (or more frequently, if necessary) of any changes in severity, the suspected relationship to the study drug, the interventions required to treat it, and the outcome.

Information about common side effects already known about the investigational drug can be found in the Investigator Brochure (IB) or Core Data Sheet (for marketed drugs) or will be communicated between IB updates in the form of Investigator Notifications. This information will be included in the subject informed consent and should be discussed with the subject during the study as needed.

The investigator should also instruct each subject to report any new adverse event (beyond the protocol observation period) that the subject, or the subject's personal physician, believes might reasonably be related to study treatment. This information should be recorded in the investigator's source documents; however, if the AE meets the criteria of an SAE, it must be reported to Novartis.

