11.1 Analysis sets

For all analysis sets, subjects will be analyzed according to the study treatment(s) received. The study has four parts, and the safety and efficacy analysis will be presented for period 1, period 2 and period 3 combined, and separately for period 4.

The safety analysis set will include all subjects that received any study drug.

The PK analysis set will include all subjects with available PK data and no protocol deviations with relevant impact on PK data.

Commercially Confidential Information

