11.5.2 Safety

Adverse events

All information obtained on adverse events will be displayed as summary and by subject as per the secondary objective.

The number and percentage of subjects with adverse events will be tabulated by body system and preferred term. A subject with multiple adverse events within a body system is only counted once towards the total of this body system.

As this study has four treatment periods an adverse event starting in period 1 and continuing into the next period is counted only in the period 1. A subject with multiple adverse events within a body system and treatment period is only counted once towards the total of this body system and treatment period. There will be three summaries of AEs, at the end of treatment period 1; periods 2 and 3 combined; and period 4.

Vital signs

All vital signs data will be listed by subject and visit/time and if ranges are available abnormalities (and relevant orthostatic changes) will be flagged. Summary statistics will be provided by visit/time.

ECG evaluations

All ECG data will be listed by subject and visit/time, and abnormalities will be flagged. Summary statistics will be provided by visit/time.

Clinical laboratory evaluations

All laboratory data will be listed by subject and visit/time and if normal ranges are available abnormalities will be flagged. Summary statistics will be provided by visit/time.

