Commercially Confidential Information

5 Statistical methods: Analysis sets

For subjects for which the actual treatment received does not match the planned treatment the treatment actually received will be used for the analysis. The study has four parts, the safety and efficacy analysis will be presented for period 1, period 2 and period 3 combined, and separately for period 4 unless otherwise stated below/in the output shell.

All subjects that received study drug will be included in the safety analysis set.

The PK analysis set will include all subjects with available PK data and no protocol deviations with relevant impact on PK data.

Commercially Confidential Information

6 Statistical methods for Pharmacokinetic (PK) parameters

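### SAP 8.1.2 assigns AEs by onset only, so one that worsens on LNP023 within its original record misses the period 4 table; it also drops the protocol's period 1 AE summary

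*SAP*

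**What the plan says.** SAP 8.1.2 (Adverse events) sets the counting rule: "an adverse event starting in one period and continuing into another is counted only in the first period grouping in which it occurs". It then plans "three types of summaries of AEs, starting in periods 1 to 3, starting in period 4, and overall throughout the study". Assignment is by onset alone, and the visible text makes no provision for an AE that gets worse later.

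Protocol 11.5.2 plans a different set: "There will be three summaries of AEs, at the end of treatment period 1; periods 2 and 3 combined; and period 4". Its carry-over rule says that "an adverse event starting in period 1 and continuing into the next period is counted only in the period 1". That covers onset in period 1 only; it is silent on an event running from period 3 into period 4.

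Protocol 11.1 says in general that "the safety and efficacy analysis will be presented for period 1, period 2 and period 3 combined, and separately for period 4". SAP section 5 has nearly the same sentence and adds the exception "unless otherwise stated below/in the output shell".

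On recording, protocol 9.1 asks for a severity grade for each AE and for "its duration (start and end dates) or if the event is ongoing an outcome of not recovered/not resolved should be reported". It also says that "assessment should be made at each visit (or more frequently, if necessary) of any changes in severity". It does not ask for the date of a severity change or say whether worsening opens a new record. For SAEs, protocol 9.2.2 has progression reported as follow-up to the original episode.

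**The concern.** Period 4 is a change of drug. Patients who may have been on LFG316 for years start LNP023, with both drugs given in the first four weeks. The period 4 table is the only AE summary in the visible plan confined to time on LNP023. A rule based on first onset is least informative at such a switch: a mild event from period 3 that turns severe on LNP023 is credited wholly to the LFG316 years.

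The regrouping is a separate matter. Tolerability of LFG316 is a secondary objective, and protocol 11.5.2 commits to an AE summary for period 1. In the SAP's tables, AEs from the first weeks of LFG316 are pooled with everything up to the end of period 3 and cannot be told apart.

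**Working it through.** The plan gives no figure to reproduce here. The check is to apply the stated rules, compare the groupings, and size the effect as far as the documents allow.

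**1. Apply the SAP rule to an example.** Take an AE that starts mild in period 3 and becomes severe after the first LNP023 dose.

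| How the site records it | Periods 1–3 table | Period 4 table | Overall table |
|---|---|---|---|
| One record, onset in period 3 | counted | not counted | counted |
| New record for the worsening, onset in period 4 | counted (first record) | counted (second record) | patient counted once per row |

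The omission arises only in the first row.

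**2. Which row applies?**
- SAEs: protocol 9.2.2 treats progression as follow-up to the earlier report. This points to the first row, although it is a reporting rule and does not describe the AE page of the CRF.
- Non-serious AEs: protocol 9.1 asks for severity changes to be assessed at visits but gives no rule on records. Either row is possible.
- SAP Modules 7 (shells) and 8 (derivations), named in SAP 1.1, are not among the documents. A worsening rule there cannot be excluded.

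**3. Compare the groupings.**

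| Source | AE summaries |
|---|---|
| Protocol 11.5.2 | period 1; periods 2–3; period 4 |
| SAP 8.1.2 | periods 1–3; period 4; overall |
| Protocol 11.1 and SAP 5 | periods 1–3 combined and period 4; or period 1, periods 2–3 and period 4, depending on how the sentence is read |

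Only period 4 is common to the first two rows. The protocol already includes period 4, so its addition does not explain the change.

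**4. Size of one omission.** One patient left out of a period 4 row changes it by 100/n percentage points, where n is the number entering period 4. Protocol 3.1 gives about 10 enrolled; the number entering is not given, so 8 and 5 are assumptions.
- n = 10: 100/10 = 10.0 points
- n = 8: 100/8 = 12.5 points
- n = 5: 100/5 = 20.0 points

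The row does not change if that patient has another AE in the same row with onset in period 4. With no AE rate in the documents, the expected number of such events cannot be computed.

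**5. Share of period 1 in the pooled window.** Protocol 3.6 gives 29 days for period 1 and 335 for period 2. The last scheduled period 3 dosing visit in Table 8-1 is Day 2185.
- Stops after period 2: 29/(29 + 335) = 29/364 = 8.0%
- Full period 3 schedule: 29/2185 = 1.3%

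These are shares of time, not of AEs. The second is a lower bound, since all LFG316 treatment was to end by the end of 2021 whatever a patient's schedule.

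**The case against.** The strongest reply is that the first part is conditional: it needs the worsening to sit in one record, and the modules that would settle this are not available. That stands for non-serious AEs. For serious ones, protocol 9.2.2 makes the condition likely. The same section also provides a safeguard: SAEs are reported within 24 hours, with relationship judged for each component of treatment. Serious worsening would therefore be seen whatever the table shows.

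It can also be said that no visible objective asks for LNP023 AE incidence, that Days 1–28 of period 4 combine both drugs so the table does not isolate LNP023, and that with about 10 uncontrolled patients the listing is the natural tool. All this is fair and keeps the point modest. It does not make a start-only table a good summary of what happened after the switch.

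On the groupings, one reading of protocol 11.1 supports the SAP, and the redacted SAP sections on first interpretable results and interim analyses might contain a period 1 output. But the AE sentences in protocol 11.5.2 and SAP 8.1.2 are both complete and visible, and they differ. An ambiguous general sentence does not override the specific one.

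Three stronger readings should be resisted:
- A reader might infer that worsened AEs are lost. They remain in the listings, the periods 1–3 table and the overall table.
- A reader might attach a probability to missing at least one patient. Any such figure would only restate an assumed AE rate.
- A reader might assume that the period 4 Day 1 visit supplies a severity grade before LNP023. In the period 4 schedule the AE row is marked as required and has no pre-dose footnote, unlike weight, ECG and laboratory tests.

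**Conclusion.** The point holds as a reporting weakness in two parts.

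First, by its own wording SAP 8.1.2 omits from the period 4 table any AE with onset in periods 1–3 that worsens after the first LNP023 dose, provided the worsening stays in the same record. That proviso is supported for SAE reporting and open for other AEs. One omitted patient is worth 10 percentage points in a row if 10 patients enter period 4, and more if fewer do. The SAP is filling a gap here, because the protocol has no rule for AEs that run from period 3 into period 4.

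Second, the AE groupings in SAP 8.1.2 contradict protocol 11.5.2. The promised period 1 summary is dropped with no reason given. This part does not depend on how records are kept.

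Neither part touches the LDH responder analysis or the proof-of-concept decision. A reader might infer that LNP023 safety would be misjudged; with full listings and expedited SAE reporting, the documents do not support that.

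**What to change.** In SAP 8.1.2:

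1. Add a listing of AEs ongoing at the first LNP023 dose: onset before that dose, and an end date on or after it or still ongoing. Show severity and relationship. Where the database holds a new record or a dated severity change, also count in the period 4 grouping any AE that increases in severity on or after the first LNP023 dose, flagged as already counted in periods 1–3.

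2. Reconcile the groupings with protocol 11.5.2, and clear up the ambiguous sentence in protocol 11.1 and SAP section 5. Either restore the period 1 AE summary alongside the SAP's three, or record its removal in the CSR as a change to the planned analysis, a route that SAP 1.2 already describes.

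The cost is SAP wording and a little programming. The listing needs only AE start and end dates and the first LNP023 dose date. The flag depends on data that the visible text does not confirm, so the listing should be planned in any case. A flagged AE appears in two groupings, so these no longer sum to the overall column; a footnote should say so.

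### Protocol and SAP name different sets of AE summaries, and the AE statistic that both describe is a crude percentage of patients, which partly reflects length of follow-up

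*SAP*

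**What the plan says.** Protocol 11.5.2 (Safety, Adverse events): "There will be three summaries of AEs, at the end of treatment period 1; periods 2 and 3 combined; and period 4".

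SAP 8.1.2 (Descriptive analyses, Adverse events): "There will be three types of summaries of AEs, starting in periods 1 to 3, starting in period 4, and overall throughout the study".

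Protocol 11.1 gives the general rule for presenting results by period: "and the safety and efficacy analysis will be presented for period 1, period 2 and period 3 combined, and separately for period 4". SAP section 5 repeats this wording and allows exceptions stated later in the SAP or in the output shells.

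On the statistic, SAP 8.1.2 says: "The number and percentage of patients with adverse events will be tabulated by body system and preferred term". Protocol 11.5.2 says the same of subjects. Both count a patient once per body system and treatment period, however many events occur.

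On events that span periods, the protocol says that "an adverse event starting in period 1 and continuing into the next period is counted only in the period 1"; the SAP says that "an adverse event starting in one period and continuing into another is counted only in the first period grouping in which it occurs".

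Exposure is handled apart from the AE tables: "Data for study drug administration, and concomitant therapies will be listed by ethnicity and C5 variant status and summarized". Individual AEs are listed in full. SAP 1.1 places the table shells in Module 7 and the derived-variable specifications in Module 8, and neither is among the public documents.

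**The concern.** Tolerability of LFG316, with heightened attention to infections, is a secondary objective, and these AE summaries are its analysis.

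First, the two current documents define those summaries differently, so a reader cannot tell from the public text which groupings the report is committed to. The SAP's overall summary would also pool LFG316 alone, both drugs together, and LNP023 alone, whereas the secondary objective names LFG316 only.

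Second, patients will be at risk for very different lengths of time. Period 2 is optional, period 3 is for patients whom the investigator judges responsive, and period 4 is for period 3 patients willing to join the extension study. A percentage of patients with at least one event rises with follow-up even if the underlying risk never changes, and it does not separate a patient with one infection from a patient with several. Without exposure beside it, the percentage cannot be read as a frequency.

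**Working it through.** **Groupings side by side**

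| Grouping | Protocol 11.5.2 | SAP 8.1.2 |
|---|---|---|
| Period 1 | named | not named |
| Periods 2+3 | named | not named |
| Periods 1–3 | not named | named |
| Period 4 | named | named |
| Overall | not named | named |

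The sentence shared by Protocol 11.1 and SAP section 5 does not settle this. It can be read as {1–3} and {4}, or as {1}, {2+3} and {4}. The exception clause in SAP section 5 makes the SAP consistent with itself but does not align it with Protocol 11.5.2.

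**Lengths, checked against the assessment schedule**

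- Period 4: 4 + 16 + 1 = 21 weeks. Day 1 to Day 148 is 147 days, or 21.0 weeks. This reproduces the stated length of about 21 weeks, of which about 20 weeks are LNP023 dosing.
- Period 3: Day 365 to Day 2185 is 1820 days, or 260 weeks, as stated.
- Periods 1–3 at most: 29 + 335 + 1820 = 2184 days, or 312 weeks. The period 1 and 2 lengths are from Protocol 3.6. The end-2021 stop will shorten this for some patients. First-dose dates are not given, so 208 weeks is used as an assumed intermediate value.
- A patient who stops after period 1 and completes the 8-week follow-up: 29 + 56 = 85 days.
- A patient who completes period 3 and its follow-up: 2184 + 56 = 2240 days. Within the SAP's periods 1–3 grouping, time at risk can therefore differ by 2240/85 = 26-fold if follow-up is counted there.
- Between groupings, the maximum lengths differ by 2184/147 = 15-fold (periods 1–3 against period 4) and by 2155/29 = 74-fold (periods 2+3 against period 1).

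**Effect on a crude percentage**

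Assume a constant infection rate r per patient-year. The documents give no rate, so a range is shown. The expected share of patients with at least one infection is 1 − exp(−r × days/365.25).

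| Time at risk | r = 0.1 | r = 0.5 | r = 1.0 |
|---|---|---|---|
| 85 days | 2.3% | 11.0% | 20.8% |
| 20 weeks (period 4 dosing) | 3.8% | 17.4% | 31.8% |
| 208 weeks | 32.9% | 86.4% | 98.1% |
| 312 weeks | 45.0% | 95.0% | 99.7% |

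For example, at r = 0.5 and 85 days: 1 − exp(−0.5 × 85/365.25) = 1 − exp(−0.116) = 0.110. Adding the 8-week follow-up to 312 weeks (2240 days) moves 95.0% only to 95.3%. In each column the risk is identical; only the duration changes.

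**Precision of the rates that would be added**

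This assumes 10 patients in each grouping; the event counts are invented for illustration.

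- Period 4, 20 weeks each: 10 × 140/365.25 = 3.83 patient-years. Two events give 2/3.83 = 0.52 per year (exact Poisson 95% interval 0.06 to 1.88).
- Period 4, Days 1–28: 10 × 28/365.25 = 0.77 patient-years.
- Periods 1–3, 208 weeks each: 10 × 1456/365.25 = 39.9 patient-years. Twenty events give 0.50 per year. With interval = rate × exp(±1.96 × √(φ/20)), the result is 0.32 to 0.78 if events are independent (φ = 1), 0.27 to 0.93 at φ = 2, and 0.23 to 1.07 at φ = 3, where φ allows for clustering of infections within patients.

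**The case against.** A reader might infer more than the documents support, in four ways.

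- **That the period 1 AE results are lost.** This cannot be asserted. The protocol's wording about the end of period 1 may refer partly to reporting time. The interim sections of both documents and the SAP's section on first interpretable results are redacted. The SAP speaks of types of summaries, keeps a counting rule by treatment period, and defers some layout to shells that are not public.
- **That no event counts or patient-years will be reported.** The public text does not mention them for AEs, but the unseen shells may include them.
- **That the two carry-over rules contradict each other.** They do not. The protocol names only events starting in period 1, and the SAP covers all periods.
- **That a patient who stops after period 1 contributes only about 4 weeks at risk.** That is the dosing time. The 8-week follow-up brings the total to 85 days, which is why the illustration uses 11% at 0.5 per year.

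It is also fair to say that the study is single-arm, descriptive and small, with no planned comparison between drugs. AEs are listed in full, with start and end dates collected, and drug administration is summarised, so rates could be worked out by hand. The period 4 interval above spans about 30-fold. On one reading of Protocol 11.1, the SAP grouping already follows the protocol's general rule.

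What stands is that Protocol 11.5.2 and SAP 8.1.2 are both current, complete sentences that differ, and that the statistic they describe does not account for time at risk. Either layout would give sound descriptive output, so the mismatch taken alone is mainly a documentation conflict.

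**Conclusion.** The point holds as a cheap improvement. The two documents share only the period 4 AE summary for a secondary endpoint, and the visible SAP text does not flag its departure from Protocol 11.5.2. The public text of both gives only the number and percentage of patients with AEs, although planned LFG316 dosing may range from about 4 to at most 312 weeks. At an assumed 0.5 infections per patient-year, duration alone moves the expected share from about 11% to 95%; at 0.1 the range is 2% to 45%, and at 1.0 it is 21% to 99.7%. These figures rest on a constant rate and on assumed lengths of follow-up, and they show the mechanism rather than predict results. No primary analysis, error rate or proof-of-concept decision is touched, and nothing here shows that planned output is missing from the full set of analysis documents.

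**What to change.** 1. In the SAP, beside the number and percentage of patients in each AE grouping, report the number of events, patient-years and events per patient-year for all AEs, infections and serious infections. Present these descriptively, because repeat infections may cluster within patients. State the time-at-risk window, including which grouping holds AEs that start in the 8-week follow-up, since the public text does not say.
2. Flag period 4 AEs by onset in Days 1–28 (both drugs) or from Day 29, and label the overall summary as covering both LFG316 and LNP023. With 0.77 patient-years, the Days 1–28 flag serves to label events, not to estimate a rate.
3. Reconcile the groupings. Either record the SAP's departure from Protocol 11.5.2 in a RAP addendum or in the CSR section on changes to planned analysis, or add the protocol's period 1 and periods 2+3 summaries to the SAP. The lists of major and minor changes in SAP 1.2 are both open-ended and neither names this case. Rewriting Protocol 11.5.2 would need a written amendment under Protocol 13.1, but none is needed for this alone.

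The cost is a few more table columns, built from dosing and AE dates already collected, and a short note. The drawback is that rates from about 10 patients will be imprecise, most of all in period 4.
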